Clarified the randomization process	Section 8.2.1	65	A total of 32 eligible healthy male and female Chinese subjects who meet the eligibility criteria will be randomized (with each gender representing no less than 1/3 of the total number) on Day 1, in a 1:1 ratio to Period 1 to one of the 2 cohorts (fasting or fed). Then each state will be randomized in a 1:1 ratio to one of 2 treatment sequences: Sequence A-B or Sequence B-A as presented in Table 5.	A total of 32 eligible healthy male and female Chinese subjects (16 in fasting cohort and 16 in fed cohort) who meet the eligibility criteria will be randomized (with each gender representing no less than 1/3 of the total number) on Day 1, in a 1:1 ratio to Period 1 to one of the 2 enhorts (fasting or fed). Then each state will be randomized in a 1:1 ratio to one of 2 treatment sequences: Sequence A-B or Sequence B-A as presented in Table 5.
Specified the condition for using oral contraceptives based upon the information in Section 6.5	Appendix I Contraceptive Guidance and Woman of Childbearing Potential	08	Highly Effective Contraceptive Methods That Are User Dependent Failure rate of < 1% per year when used consistently and correctly. Combined (estrogen- and progestogen- containing) hormonal contraception associated with inhibition of ovulation ^b ovulation ^b intravaginal transdermal	Highly Effective Contraceptive Methods That Are User Dependent Failure rate of < 1% per year when used consistently and correctly. Combined (estrogen- and progestogen- containing) hormonal contraception associated with inhibition of ovulation ^b oral (not allowed for women taking part in the study but allowed for female partners of male volunteers) intravaginal transdermal
Administrative change on clinical team lead	Appendix II	84	Name, academic degree Function / Title: PPD Merck Serono (Beijing) Pharmaceutical Institution R&D Co., Ltd.	Name, academic degree PPD PPD PPD PPD PPD PPD PPD Function / Title: PPD

Bioequivalence Trial of Concor AM^{\circledast} vs Bisoprolol and Amlodipine in Chinese Subjects Bisoprolol & Amlodipine EMR200006-001

Change	Section	Page		Previous Wording		New Wording
	Sponsor Responsible		Address	Merck Serono Co., Ltd. PPD	Institution	Merck Serono (Beijing) Pharmaceutical R&D Co., Ltd. March Serono Co. 144
	Persons not Named on the				Addless	PPD
	Cover Page		Telephone number	OPPO		
			Fax number E-mail address	PPD PPD		
					Telephone number	Odd
					Fax number	РРД
						РРД
					E-mail address	PPD

e Bioequivalence Trial of Concor AM® vs Bisoprolol and Amlodipine in Chinese Subjects

Bisoprolol & Amlodipine EMR200006-001

Update on Table 1 Schedule of Assessments

Assessmentsª	Scr	Screening				Per	Period 1								H	Period 2	12				End of Trial	End Prematur of Withdra
Day	-7 ~ -2	-1 Admission	1 ^b	2 3	3 4	5	9	7 1	8 Discharge	9-13	14 Admission	15 ^b	16	17	18	19	20	21	22 Discharge	23-28	29	
Informed consent form signed	X																					
Demographic information	X																					
Inclusion/exclusion criteria	X																					
History of alcohol and nicotine consumption	X																					
Medical history	X																					
Prior medications	Xc																					
Laboratory tests	X								X		X								Х			X
Serum Pregnancy test (only for females of child-bearing potential)	X								X										Х			×
HIV antibody, HBsAg, HCV antibody, and TP antibody tests	X																					
Urine screening of drugs of abuse and breath test of alcohol	X	X									Х											
Urine nicotine	X																					
Randomization			X						*													
Drug administration			X									X										
Blood sampling for Pharmacokinetics ^d			×	×	×	×	×	×	×			×	×	×	×	×	×	×	×		×	×

Bioequivalence Trial of Concor AM® vs Bisoprolol and Amlodipine in Chinese Subjects Bisoprolol & Amlodipine

EMR200006-001

Assessmentsa	Scr	Screening				Pel	Period 1	-							Ъ	Period 2	12				End of Trial	End Prematur of Withdra wal
Day	-7 ~ -2	$^{-7}$ $^{-1}$ Admission	1 ^b 2	1.00	8	5	3 4 5 6 7		8 Discharge	9-13	14 Admission 15 ^b 16 17 18 19 20 21	15 ^b	16	17	18	19	20	21 D	22 Discharge	23-28 29	29	
Physical examination	X	X							X		X								X			X
Vital signs (blood pressure, pulse rate, temperature and respiration)*	X	Х	хх	50000	X X	₩	×		х		x	×	×	X X X	×		×		x			×
Electrocardiogram^f	X	X	X	1000	X				X		X	X		X					X			X
Chest X-ray	X								X										X			X
AEs and concomitant therapies ²											Continuous	SI										

AE = adverse event; HBsAg = hepatitis B surface antigen; HCV = hepatitis C virus; HIV = human immunodeficiency virus; TP = treponema pallidum

Subject will participate in the clinical trial on an in-house basis during Day -1 to Day 8 and also during Days 14 to 22. Subjects are excused from the clinic during certain days after each period: from trial Day 9 to Day 13 and from trial Day 23 to Day 28.

After the single dose administration, Washout begins.

Prior medication within 1 month before the date of first signature of informed consent will be collected.

[figure not shown]
For every subject, during each treatment period, pharmacokinetic blood samples will be collected at the following times: at predose (Baseline) and at 0.5, 1, 1.5, 2, 3, 4, 6, 8, 10, 12, 15, 24, 36, 48, 72, 96, 120, 144, and 168 hours after dosing. One sample will be collected at End of Trial (Day 29) or Premature Withdrawal.

Vital signs will be taken at Screening, at admission (Day -1 and Day 14), prior to dosing and also at 4, 8, and 12 hours postdose at Day 1 and Day 15; and before blood sampling at Day 2, 3, 4, 6, and 8 in Period 1, then Day 16, 17, 18, 20, and 22 in Period 2, and at Premature Withdrawal (if applicable).

Electrocardiograms will be taken at Screening, at admission (Day -1 and Day 14), prior to dosing and also at 4 hours postdose at Day 1 and Day 15; at 48 hours postdose at Day 3 and Day 17; then at discharge of each period (Day 8 and Day 22), and at Premature Withdrawal (if applicable).

AEs and concomitant therapies will be collected continuously from the date of first signature of informed consent.

Schematic of Trial Design Update on Figure 1 EMR200006-001

Section 7.1.9 (Estimated Blood Sample Volumes per Subject) with Table 4

The blood sample volumes of each subject are estimated in Table 4.

Table 4 Estimated Blood Sample Volumes per Subject

Time Points	Evaluation Indexes	Total Blood Volume (mL
	Serum virology	4
	Hematology	2
Screening	Biochemistry	4
Screening	Serum Pregnancy Test (if applicable)	4
	Approximate Total	14
	Hematology	2
	Biochemistry	4
Period 1	Serum Pregnancy Test (if applicable)	4
	Pharmacokinetics	45 *20
	Approximate Total	110 90
	Hematology	2*2
	Biochemistry	4*2
Period 2	Serum Pregnancy Test (if applicable)	4
	Pharmacokinetics	45 *20
	Approximate Total	116 96
End of Trial	Pharmacokinetics	45
	Approximate Total	45
	Hematology	2
	Biochemistry	4
Premature Withdrawal	Serum Pregnancy Test (if applicable)	4
	Pharmacokinetics	4 5
	Approximate Total	 1514
Approximate Total of Each Swithdrawal)	ubject (without premature	245 204

## 3 List of Abbreviations and Definition of Terms

Abbreviation	Definition
AE	Adverse Event
AUC	Area under the plasma concentration-time curve
$AUC_{0-\infty}$	The AUC from time zero (dosing time) extrapolated to infinity
AUC 0-t	The AUC from time zero (= dosing time) to the last sampling time ( $t_{last}$ ) at which the concentration is at or above the lower limit of quantification
AUC extra %	The AUC from time $t_{last}$ extrapolated to infinity given as percentage of $AUC_{0-\infty}$
BE	Bioequivalence
CI	Confidence Interval
$\mathrm{CL}/\mathrm{f}$	The apparent total body clearance of drug following extravascular administration.
$C_{max}$	Maximum observed plasma concentration
CRO	Contract Research Organization
CSR	Clinical Study Report
CTR	Clinical Trial Report
CTMS	Clinical Trial Management System
CTP	Clinical Trial Protocol
CV	Coefficient of Variation (%)
ECG	Electrocardiogram
ECOG	Eastern Cooperative Oncology Group
eCRF	Electronic Case Report Form
GCP	Good Clinical Practice
GeoCV%	Geometric Coefficient of Variation
GeoMean	Geometric Mean
HR	Hazard ratio
ICF	Informed Consent Form
ICH	International Conference on Harmonization
IMP	Investigational Medicinal Product
LLOQ	Lower Level of Quantification

## Bisoprolol Amlodipine 5 mg/5 mg Combination Tablets EMR200006-001

## Two-period Crossover Bioequivalence Final Version 2.2

Max Maximum

Mean Arithmetic mean

Min Minimum

MedDRA Medical Dictionary For Regulatory Activities

MRI Magnetic Resonance Imaging

N Number of non-missing observations

PK Pharmacokinetics
PR Partial Response
PT Preferred team

SAE Serious Adverse Event
SAP Statistical Analysis Plan
SBP Systolic Blood Pressure
SD Standard Deviation

SDTM Study Data Tabulation Model
SEM Standard Error of the Mean

SOC System Organ Class

t1/2 Apparent terminal half-life

TEAE Treatment-Emergent Adverse Event

tlast The last sampling time at which the concentration is at or above

the lower limit of quantification

 $t_{max}$  The time to reach the maximum observed concentration

 $V_{z/f}$  Apparent volume of distribution during the terminal phase

following extravascular administration

 $\lambda_z$  Terminal elimination rate constant

## 4 Modification History

Unique Identifier for SAP Version	Date of SAP Version	Author	Changes from the Previous Version	
Draft V0.1	02Jun2017	PPD	Not Applicable – First Version	
Final V1.0	28Jun2017	PPD	Update per internal comments	
Final V1.1	26Jul2017	PPD	Update per sponsor's comments	
Final V1.2	08Aug2017	PPD	Update per sponsor's comments	
Final V2.0	01Sep2017	PPD	Update per sponsor's comments	
Final V2.1	13Sep2017	PPD	Update per sponsor's comments	
Final V2.2	18Sep2017	PPD	Update per sponsor's comments	

## 5 Purpose of the Statistical Analysis Plan

The purpose of this Statistical Analysis Plan (SAP) is to document technical and detailed specifications for the final analysis of data collected for protocol EMR200006-001. Results of the analyses described in this SAP will be included in the Clinical Study Report (CSR). Additionally, the planned analyses identified in this SAP will be included in regulatory submissions or future manuscripts. Any post-hoc, or unplanned analyses performed to provide results for inclusion in the CSR but not identified in this prospective SAP will be clearly identified in the CSR.

The SAP is based upon Section 8 (Statistics) of the trial protocol and protocol amendments and is prepared in compliance with ICH E9.

	• Drug administration will be done with or without food depending on cohort allocation to either fasting or fed state. The subjects will remain in the same group (fasting or fed) in both treatment periods.				

[figure not shown]
	In each group (fed and fasted), the subjects were randomized to one of 2 treatment sequences: A-B or B-A.			
Planned number of subjects	A total of 32 healthy male and female Chinese subjects will be enrolled in the trial, with each gender representing no less than 1/3 of the total number (also evenly allocated to fasting vs. fed group). Sixteen subjects each will be enrolled into the fasting group and fed group, respectively, and statistically powered to provide adequate sample size for BE testing. Each subject will be administered both the investigational product and comparators in this 2 × 2 crossover BE trial to minimize the effect of the individual difference and periodic difference of the testing results.			
Treatment and Trial Duration	The trial has a duration of approximately 5 weeks for the fasting or fed group respectively for each subject, including:			
	• Screening (assessments to determine eligibility for entry into the trial; occurring from Day -7 to Day -1)			
	Admission to the Clinical Research Unit (CRU) on Day -1			
	• Period 1 (duration of 8 days; Day 1-8)			
	• Washout (duration of 14 days; Day 1-14)			
	• Admission to the CRU on Day 14			
	• Period 2 (duration of 8 days; Day 15-22)			
	Washout (duration of 14 days; Day 15-28)			
	End of Trial (visit occurring after the second 14-day washout on Day 29) or premature withdrawal from the trial.			
Pharmacokinetics	The plasma concentrations of bisoprolol and amlodipine will be determined by a validated analytical method using HPLC with MS/MS detection. Pharmacokinetic parameters (primary and secondary endpoints) will be calculated according to non-compartmental analysis methods. The mixed trapezoidal rule will be used to calculate the area under the plasma concentration curve.			
Randomization and Blinding	As this is an open-label trial, no method of blinding was used. Subjects were randomly assigned to one of the 2 treatment sequences (A-B, B-A) per group. Randomization occurred immediately before dosing on Treatment Period 1/Day 1.			

## 7 Sample Size/Randomization

achieved.

The BE is declared if all comparisons in primary hypothesis achieve the criteria – the 90% CIs for the ratios between the investigational product and comparators of geometric means of both  $AUC_{0-t}$  and  $C_{max}$  for bisoprolol and amlodipine in plasma are within 80.00% to 125.00%.

Based on the results of a BE trial conducted in 2008 by PPD where a higher dose strength 10 m/10 mg fixed-dose-combination tablet was tested against respective single agent of bisoprolol and amlodipine, the expected effects in fasting state is presented below.

## Sample Size and Power Calculation Results

will be enrolled. In the case of full completion by all 16 subjects, a power of > 90% may be

Sample Size	Power (%) for Bisoprolol		Power (%) for Amlodipine		Joint Power (%)
1	$C_{max}$	AUC 0-t	$C_{max}$	AUC 0-t	
10	100.00	99.59	96.27	74.30	71.24
12	100.00	99.92	98.56	82.13	80.88
14	100.00	99.98	99.46	87.71	87.22
16	100.00	100.00	99.80	91.63	91.45

 $AUC_{0-t}$  = area under the (plasma) concentration-time curve from time 0 to time t;  $C_{max}$  = the maximum plasma concentration observed

Historical data showed no food effect on PK for either drugs, bisoprolol and amlodipine respectively [1, 2], and the observed variability has been comparable between fasting and fed dosing states. By applying statistical powering also to the fed group, assuming the intra-subject variability is similar in fed state with standard meal consumption [1, 2]. Based on the sample size calculation above, a 16-subject trial (12 subjects with adequate power and 4 subjects to cover potential dropout) provides at least 80% power to meet the BE criteria for both parameters and both products.

Sensitivity analysis has been performed to explore impact of potentially different variability on the sample size and power calculation. The outcome, as selectively displayed in the tables below, suggests that consistently high power (80%+) can be obtained with the proposed sample size.

#### Sensitivity Analysis 1:

Assume 5% variation for all ratios (95%  $\sim$  105%) and 10% all intra-subject CV.

Samula Siza	Power (%) for Bisoprolol		Power (%) for Amlodipine		Laint Daway (0/)
Sample Size	Cmax	AUC 0-t	Cmax	AUC 0-t	Joint Power (%)
10	96.83	96.83	96.83	96.83	87.89
12	98.83	98.83	98.83	98.83	95.42
14	99.58	99.58	99.58	99.58	98.34
16	99.85	99.85	99.85	99.85	99.42

 $AUC_{0-t}$  = area under the (plasma) concentration-time curve from time 0 to time t; CV = coefficient of variation;  $C_{max}$  = the maximum plasma concentration observed

#### Sensitivity Analysis 2:

Assume 5% variation for all ratios (95%  $\sim$  105%) except of Amlodipine AUC0-t (90%  $\sim$  110%), and 10% all intra-subject CVs.

Sample Size	Power (%) for Bisoprolol		Power (%) for Amlodipine		Laint Dawan (9/)
Sample Size	Cmax	AUC 0-t	Cmax	AUC 0-t	Joint Power (%)
10	96.83	96.83	96.83	77.74	70.56
12	98.83	98.83	98.83	85.17	82.23
14	99.58	99.58	99.58	90.25	89.13
16	99.85	99.85	99.85	93.66	93.26

 $AUC_{0-t}$  = area under the (plasma) concentration-time curve from time 0 to time t;  $C_{max}$  = the maximum plasma concentration observed

Each eligible subject will be allocated to a treatment sequence according to a computergenerated randomization schedule. Subjects will be identified only by their assigned subject number. The subjects will receive consecutive subject numbers in the order of their enrollment into the trial.

A total of 32 eligible healthy male and female Chinese subjects (16 in fasting group and 16 in fed group) who meet the eligibility criteria will be randomized (with each gender representing no less

than 1/3 of the total number) on Day 1 in a 1:1 ratio to one of 2 treatment sequences: Sequence A-B or Sequence B-A.

In Sequence A-B, subjects will receive bisoprolol-amlodipine 5 mg/5 mg combination tablets (Treatment A) in Period 1 and bisoprolol 5 mg tablets and amlodipine 5 mg tablets given concomitantly (Treatment B) in Period 2. In Sequence B-A, subjects will receive bisoprolol 5 mg tablets and amlodipine 5 mg tablets given concomitantly (Treatment B) in Period 1 and bisoprolol amlodipine 5 mg/5 mg combination tablets (Treatment A) in Period 2.

The first 4 discontinued subjects of each group will not be replaced. Subjects will only be replaced if the number of subjects within a sequence falls below 12. The subject who is replacing a discontinued subject will then be allocated to the treatment sequence of the subject who discontinued.

## 8 Overview of Planned Analyses

The methods described in this document will be applied to the preparation of tables, figures and listings (TLFs). Statistical analyses will be performed using cleaned electronic clinical report form (eCRF) data collected.

This SAP will cover the final analysis only. The final analysis will be performed only after the last subject has completed the study with all study data in-house and all data queries resolved. The SAP will be finalized prior to database lock.

## 9 Changes to the Planned Analyses in the Clinical Trial Protocol

The Screening Analysis Set has been added to include all subjects who signed informed consent in the study. The per-protocol population has been removed.

The PK parameter, apparent volume of distribution at steady-state after extravascular administration ( $V_{ss}/f$ ) was originally proposed in the CTP (Clinical Trial Protocol). However, this PK parameter cannot be calculated based on the dosing regimen (i.e., single dose) and route of administration (i.e., oral). As such, the apparent volume of distribution during the terminal phase following extravascular administration ( $V_z/f$ ) will be calculated instead to provide an estimate of the extent of drug distribution following a single oral dose.

## 10 Protocol Deviations and Analysis Sets

## 10.1 Definition of Protocol Deviations and Analysis Sets

Protocol deviations describe how closely the study has been conducted according to the protocol as expected per GCP. Some of these deviations may be significant contributors to analysis bias.

Important protocol deviations are protocol deviations that might significantly affect the completeness, accuracy, and/or reliability of the study data or that might significantly affect a subject's rights, safety, or well-being.

Examples of clinically important protocol deviations or important events for PK include, but may not be limited to, the following:

- Subjects that are dosed on the study despite not satisfying the inclusion criteria;
- Subjects that develop withdrawal criteria whilst on the study but are not withdrawn:
- Subjects that receive the wrong treatment or an incorrect dose;
- Subjects that receive an excluded concomitant medication;
- Deviation from GCP.
- Adverse events, vomiting, diarrhea, etc.
- Vomiting following oral dosing (these instances will be discussed on a case-by case basis)
- Sample processing errors that may lead to inaccurate bioanalytical results
- Inaccurate dosing or dosing errors
- Incomplete meal consumption prior to dosing
- Concomitant medication violations

The following deviations will be identified and confirmed prior to or at the Data Review Meeting at the latest. Important protocol deviations include

- Deviations from the inclusion and exclusion criteria
- Deviations post inclusion

A data review will be held to discuss and update the definition of important protocol deviations so as to determine the evaluability of the subjects prior to database lock.

## 10.2 Definition of Analysis Sets and Subgroups

Screening Analysis Set

The Screening Analysis Set includes all subjects who have signed the main informed consent (i.e., screening failures plus subjects enrolled).

Safety Analysis Set

The Safety Analysis Set includes all subjects who received at least 1 dose of trial drug. In general, clinical data will be analyzed for the Safety Analysis Set.

Pharmacokinetic Analysis (PK) Set

The PK Analysis Set includes all subjects who completed the trial with adequate trial medication compliance, without any relevant protocol violations or events with respect to factors likely to affect the comparability of PK results, and with sufficient evaluable data to determine primary endpoints (AUC $_{0-t}$  and  $C_{max}$ ) for both treatments and analytes. If subjects receive concomitant medication that potentially affects PK for the treatment of an AE, their inclusion in the PK Analysis Set will be decided on a case-by-case basis. Emesis occurring within two times of the median  $t_{max}$  for a given analyte and the treatment will be considered a relevant event likely to affect the comparability of PK results. Similarly, a predose concentration for a given analyte and treatment

period which exceeds 5% of Cmax will be considered a relevant event affecting PK results. All PK analyses will be based on the PK Analysis Set.

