8.2.3 Analysis Sets

Per-protocol population

The per-protocol population includes all randomized subjects who have been treated according to protocol and fulfill the following criteria:

- All inclusion/exclusion criteria satisfied, unless some criteria were waived by the Investigator/Sponsor
- Absence of relevant protocol violations with respect to factors likely to affect the comparability of PK results
- Adequate investigational product compliance
- Primary PK variables AUC_{0-t} and C_{max} of bisoprolol or amlodipine in plasma should be available for both trial treatments

If subjects received concomitant medication for the treatment of AEs within 48 hours after dosing, their inclusion in the per-protocol population should be approved by the Sponsor.

Safety population

The safety population includes all subjects who received at least 1 dose of trial drug. In general, clinical data will be analyzed for the safety population.

Pharmacokinetic population

The PK Population may include all subjects who completed the trial with adequate trial medication compliance, without any relevant protocol violations with respect to factors likely to affect the comparability of PK results, and with sufficient evaluable data to determine primary endpoints (AUC_{0-t} and C_{max}) for both treatments in both cohorts. If subjects would receive concomitant medication for the treatment of an AE, their inclusion in the PK Population will be decided on a case-by-case basis. All PK analyses will be based on this population analysis set.

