## 16 Endpoint Evaluation

## 16.1 Primary Endpoint Analyses

The primary endpoints are the following PK parameters calculated from bisoprolol and amlodipine plasma concentrations:

- AUC0-t of bisoprolol
- Cmax of bisoprolol
- AUC0-t of amlodipine
- Cmax of amlodipine

groups

The null and alternative hypotheses are as follows:

```
\begin{split} H_0: & \textit{for AUC}_{0-t} \ \ \mu_T \ / \ \mu_C \leq 0.8 \ \textit{or} \ \mu_T \ / \ \mu_C \geq 1.25 \\ & \textit{for C}_{\max} \ \ \mu_T \ / \ \mu_C \leq 0.8 \ \textit{or} \ \mu_T \ / \ \mu_C \geq 1.25 \end{split}, \text{ for at least 1 primary endpoint} \\ H_1: & \textit{for AUC}_{0-t} \ \ 0.8 < \mu_T \ / \ \mu_C < 1.25 \\ & \textit{for C}_{\max} \ \ \ 0.8 < \mu_T \ / \ \mu_C < 1.25 \end{split}, \text{ for all 4 primary endpoints and for both fasting and fed} \end{split}
```

where  $\mu_T$  and  $\mu_C$  are the geometric means of the primary endpoints following investigational product (Treatment A) and comparators (Treatment B), respectively.

The analysis of primary endpoints will be based on the PK Population (Section 10.2)

The primary endpoints, Cmax and AUC0-t in fasting or fed group, will be log-transformed and a mixed-effects model will be applied. The model will include fixed effects for sequence, treatment, and period and a random effect of subject nested within sequence. Treatment differences on the log scale will be estimated for the parameters together with their 90% CIs. The least squares means together with their 95% CIs by treatment will also be estimated. Point estimates and CIs will be back-transformed to the original scale for presentation, i.e., ratios of geometric means and corresponding 90% CIs for Treatment A/Treatment B, geometric means and corresponding 95% CIs by treatment, respectively. Intra-subject CV estimated from the model will also be presented. The BE will be established if all 4 sets of the 90% CIs for the ratios of geometric means between the investigational product and the comparators fall within 80.00% to 125.00%.

The following example code could be used:

```
proc mixed data=pkparam;
by food analyte param;
class sequence period trt subjid;
model lnest = sequence period trt /ddfm=kr;
random subjid(sequence);
estimate 'A vs B' trt 1 -1 /alpha=0.1 cl;
lsmeans trt /alpha=0.05 cl;
```

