## Bisoprolol Amlodipine 5 mg/5 mg Combination Tablets EMR200006-001

Two-period Crossover Bioequivalence Final Version 2.2

Samples that are collected outside the specified time windows will be included in the PK analysis but excluded from the concentration summary. The PK sampling collection schedule is presented in Table 1 below.

Table 1 Pharmacokinetic Sample Collection Schedule

Trial Day	Period Day	Time of Blood Sample (hour)	Window Allowance (minute)
1	1 - Predose in Period 1	Baseline blood draw (10 minutes prior to drug administration)	±2
1	1 – Single dose administration and Washout begins	0.5, 1, 1.5, 2, 3, 4, 6, 8, 10, 12, 15	±2
2	2	24, 36	±5
3	3	48	±5
4	4	72	±30
5	5	96	±30
6	6	120	±30
7	7	144	±30
8	8	168	±30
9 - 14			
15	1-Predose in Period 2	Baseline blood draw (10 minutes prior to drug administration)	±2
15	1- Single dose administration and Washout begins	0.5, 1, 1.5, 2, 3, 4, 6, 8, 10, 12, 15	±2
16	2	24, 36	±5
17	3	48	±5
18	4	72	±30
19	5	96	±30
20	6	120	±30
21	7	144	±30
22	8	168	±30
23 - 28			
End of Trial (Day 29)/Premature Withdrawal		1-sample	±30

Arithmetic mean plasma bisoprolol and amlodipine concentration versus scheduled (nominal) time plots will be provided for each treatment and food condition using a linear and semi-logarithmic scale. Mean plots will include SD error bars ( $\pm$ SD) when plotted on a linear scale. The mean plasma concentration-time profiles will be plotted for subjects included in the respective PK Analysis Set.

Individual plasma bisoprolol and amlodipine concentration versus actual time plots will be provided for each treatment by food condition using a linear and semi-logarithmic scale. Plots of individual profiles of plasma bisoprolol and amlodipine concentration versus actual time for all subjects within each treatment, presented on a single plot (i.e., spaghetti plots), will be provided by Fed/Fasting group, separately, using a linear and semi-logarithmic scale. All statistical analyses and descriptive summaries of PK data will be performed on the PK Analysis Set. Pharmacokinetic concentrations will be listed for all subjects by treatment and group; concentrations excluded from the PK analysis will be flagged within the listing

A listing of PK blood sample collection times by individual, as well as derived sampling time and time deviations, will be provided.

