# 16.3.2 Estimation of Individual Pharmacokinetic Parameters by Noncompartmental Analysis

For the PK analysis, predose sample concentrations that are missing will be assigned a numerical value of zero for the calculation of AUC. Any anomalous concentration values observed at predose will be identified in the CTR, and if the anomalous predose concentration value is greater than 5.00% of the  $C_{max}$  in the profile, the profile will be excluded from summaries and inferential statistics as appropriate; handling of the data will be documented in the CTR. Pharmacokinetic parameters for the affected profile shall be calculated as part of the WinNonlin® run and will be listed.

Pharmacokinetic parameters will be calculated using standard non-compartmental methods. Pharmacokinetic parameters will be evaluated and listed for all volunteers who provide sufficient concentration-time data. At least 3 valid, postdose concentration points will be required in the PK profile to obtain any PK parameter estimate.

Pharmacokinetic parameters will be calculated using the actual elapsed time since dosing, given with a precision of 14 significant digits or the SAS format Best12. In cases where the actual sampling time is missing, calculations will be performed using the scheduled time. Otherwise, there will be no further imputation of missing data other than for a missing predose concentration as stated above.

For each subject in the PK Analysis Set the following PK parameters will be calculated for bisoprolol and amlodipine, where appropriate:

Symbol	Definition
AUC 0-t	The area under the concentration-time curve (AUC) from time zero (= dosing time) to the last sampling time ( $t_{last}$ ) at which the concentration is at or above the LLOQ. Calculated using the mixed log linear trapezoidal rule (linear up, log down). Units: $ng*h/mL$ .

Symbol	Definition
AUC 0 -∞	The AUC from time zero (dosing time) extrapolated to infinity, based on the predicted value for the concentration at $t_{last}$ , as estimated using the linear regression from $\lambda_z$ determination. $AUC_{0-\infty} = AUC_{0-t} + C_{last  pred} / \lambda_z$ . Units: $ng*h/mL$ .
AUC extra %	The AUC from time $t_{last}$ extrapolated to infinity given as percentage of $AUC_{0-\infty}$ . $AUC_{extra\%} = (extrapolated area/AUC_{0-\infty})*100$ . The predicted $AUC_{0-\infty}$ should be used. Units: %.

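### SAP 10.2 makes PK evaluability all-or-nothing per subject, so a failure confined to one analyte needlessly removes the other analyte's valid pair from separately fitted BE models

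*SAP*

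**What the plan says.** SAP 10.2 admits a subject to the PK Analysis Set only if there are enough data for AUC0-t and Cmax "for both treatments and analytes". It then states: "All PK analyses will be based on the PK Analysis Set". Among the events that count against inclusion are emesis within twice the median tmax and "a predose concentration for a given analyte and treatment" period above 5% of Cmax. Both are worded per analyte but act as criteria for a set of subjects.

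Other SAP sections work at a finer level:

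- The example code in SAP 16.1 runs the mixed model "by food analyte param", so each analyte has its own model.
- For a predose value above 5% of Cmax, SAP 16.3.2 says that "the profile will be excluded from summaries and inferential statistics as appropriate".
- SAP 16.3.1 says that the mean curves "will be plotted for subjects included in the respective PK Analysis Set", which suggests more than one set. Only one is defined.

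**The concern.** The analysis does not need a common set of subjects. A subject with sound amlodipine data in both periods contributes a complete within-subject pair to the amlodipine models, whatever happened to bisoprolol. The all-or-nothing rule discards that pair.

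The loss matters most on amlodipine AUC0-t. The protocol synopsis names it as the endpoint that drives the sample size, and it has the lowest power in the plan's table. All four confidence intervals must lie within 80.00% to 125.00%, so lost power on this endpoint lowers the chance of showing bioequivalence.

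There is also an ambiguity. For the same predose event, SAP 10.2 can be read as removing the subject and SAP 16.3.2 as removing one profile. The N of a primary analysis would then depend on which section is followed. In an open-label trial this should be settled before the data are reviewed.

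**Working it through.** **Inputs.** For amlodipine AUC0-t the ratio is 111.22% and the within-subject CV 10.4% (protocol synopsis, statistical methods). The limits are 80.00% to 125.00% with 90% intervals (SAP 7), that is, two one-sided 5% tests. Each cohort has 16 subjects, 8 per sequence: 12 evaluable plus 4 for dropout.

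**Formulas.** On the log scale, s = √ln(1 + CV²) = √ln(1.010816) = 0.1037. With n₁ and n₂ subjects per sequence, SE = s·√[(1/n₁ + 1/n₂)/2] and df = n₁ + n₂ − 2. The distance from the assumed ratio to the upper limit is ln 1.25 − ln 1.1122 = 0.2231 − 0.1063 = 0.1168. Power is the exact probability that both one-sided tests reject.

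**Reproducing the plan.** For n = 10, 12, 14 and 16 this gives 74.30%, 82.13%, 87.71% and 91.63%, the same as the SAP 7 table. The stated joint powers are the products of the four marginal powers, for example 1.0000 × 0.9992 × 0.9856 × 0.8213 = 80.88% at n = 12.

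**Cost of one amlodipine pair lost because of bisoprolol.**

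| Evaluable n (by sequence) | SE | Power, amlodipine AUC0-t |
|---|---|---|
| 16 (8/8) | 0.0367 | 91.63% |
| 15 (8/7) | 0.0380 | 89.73% |
| 12 (6/6) | 0.0423 | 82.13% |
| 11 (6/5) | 0.0444 | 78.24% |

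The loss is 91.63 − 89.73 = 1.90 points from full completion, and 82.13 − 78.24 = 3.89 points from the planned minimum.

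**Effect on joint power at the minimum.** Suppose 12 subjects are otherwise evaluable and one has a bisoprolol-only failure.

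- Under SAP 10.2 as written, joint power cannot exceed 78.24%.
- With per-analyte evaluability, amlodipine stays at 12 and bisoprolol falls to 11. Taking the n = 10 bisoprolol AUC0-t power as a lower bound, the plan's product rule gives at least 1.0000 × 0.9959 × 0.9856 × 0.8213 = 80.6%.

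**How a bisoprolol-only failure could arise.**

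- *Emesis:* hardly possible. On the tmax ranges in protocol Sections 3.1 and 3.2, twice tmax is 4–8 h for bisoprolol and 12–24 h for amlodipine. Emesis inside the first window is also inside the second.
- *Carry-over:* negligible. A 14-day washout is 336 h, which is 28 to 33.6 bisoprolol half-lives of 12 to 10 h.
- *What remains:* a bisoprolol assay failure, or bisoprolol data judged insufficient at the data review.

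The reverse case, an amlodipine-only failure that removes a bisoprolol pair, costs little. Bisoprolol power is at least 99.59% even at n = 10.

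**The case against.** The strongest defence is that one population is a reasonable choice for a two-component product. All four intervals must pass, and a single set gives one N for the joint claim. The rule introduces no bias that can be shown from the documents and does not raise the type I error. Both analytes come from the same blood samples, so most sample problems affect both, and the back-up vial covers many assay failures. The reserve of four subjects absorbs isolated losses. All of this stands, and it limits the size of the point. It does not explain the all-or-nothing rule, since neither document gives a reason for a common set, and it does not reconcile SAP 10.2 with 16.3.1 and 16.3.2.

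A reader might infer two stronger things that the documents do not support.

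- *That missed samples around the bisoprolol peak disqualify the subject.* No rule says so. SAP 16.3.2 asks for at least 3 valid postdose concentrations and takes Cmax as the observed maximum. Without the 1.5, 2, 3 and 4 h samples, 15 of the 19 postdose samples remain. Cmax would be less well captured but still determinable. Only a judgement at the data review could exclude it.
- *That the SAP silently tightened the protocol.* The protocol's per-protocol set did ask only that the primary variables "of bisoprolol or amlodipine in plasma should be available for both trial treatments", but it was never the primary analysis set, and SAP Section 9 declares its removal. Protocol Section 8.2.4.2 bases the primary analysis on the PK population, which requires data to determine the primary endpoints "for both treatments in both cohorts". Protocol Section 8.2.2.1 lists four such endpoints, two per analyte, so the SAP wording may only make that explicit.

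**Conclusion.** The point holds as a weakness in the definition of the analysis set. SAP 10.2 ties the two analytes together where the models do not, and other SAP sections work by profile or imply separate sets. A valid pair for one analyte can be lost for a reason that concerns only the other.

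The effect is modest. One such loss costs about 2 points of amlodipine AUC0-t power at full completion. It takes that power below 80% only if four other subjects in the cohort have already been lost. These figures assume the plan's ratio of 1.1122 and CV of 10.4%, and near-equal sequences. The documents give no rate of single-analyte failure, so the expected loss cannot be computed. The remaining routes suggest that it is small.

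**What to change.** In SAP 10.2, define PK evaluability per analyte. A subject enters the models for an analyte if AUC0-t and Cmax of that analyte are determinable for both treatments, and non-evaluability of one analyte does not remove the other. Apply the emesis and predose criteria to the analyte concerned.

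Align SAP 16.3.1 and 16.3.2 with this, so that the respective set and the profile exclusion refer to the same rule. Report N per analyte in each food group, and record the rule in SAP Section 9 before database lock. If a common set is intended, state that and the reason for it, and make 16.3.1 and 16.3.2 agree.

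The cost is SAP wording and one analyte-level flag in the analysis data. N may then differ between the bisoprolol and amlodipine tables.
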